## 5. Study Design

LIFEGUARD is a prospective, post-market interventional, pilot study. Approximately 210 patients will be enrolled in two European centers.

The study will consist of two phases. During both phases the patients will be 1:1 randomly allocated to Capnostream20p or to PM1000N-RR monitoring. The Capnostream 20p device provides data on etCO2, RR, SpO2, PR and IPI through an oral/nasal cannula and a finger sensor, while PM1000N-RR provides SpO2, PR and RR derived from plethysmography through a single finger sensor. The aim of the random allocation is to have similar patient populations receiving monitoring with the two different devices.

During the study Phase I, 70 patients will be enrolled and the alarms of both devices will be silenced and the screen information blinded, to establish the incidence of respiratory events, as is the current clinical practice in which continuous monitoring is not employed. After Phase I and before the start of study Phase II, each participating site will have a minimum of one month to familiarize themselves with the unblinded device, using a pre-defined hospital protocol for alarm management and escalation policy.

During the study Phase II, an additional 140 patients will be enrolled; but in this phase the screen information will be available, and the nursing staff will be instructed to respond to both devices' alarms based on a pre-defined hospital protocol.

During both phases, each patient will be monitored for a minimum of 24 hours and up to patient's full mobilization or for a maximum of 72 hours. At the end of the monitoring period the patient will complete the study and will continue to be treated according to standard clinical practice. Figure 1 reports the study Flow-Chart.

A survey will be conducted at the end of the study amongst the participating physicians and nurses to assess levels of their satisfaction and patient compliance with the two different monitoring technologies and the overall feasibility of continuous respiratory monitoring in a general ward setting.

[figure not shown]
Capnography and pulse oximetry monitoring device data will be collected as well as clinical data related to respiratory compromise. Patients will be monitored per standard of care.

Enrollment at any single site will be limited to 50% (approximately 105 patients) to ensure poolability of the data across sites and reduce potential bias. Additional methods incorporated to minimize potential bias include the following:

[figure not shown]
- Systematic identification of potential patients via screening;
- Standard procedures and data collection requirements with a common electronic database for all sites;
- Random allocation to monitoring device.

Foreseeable factors that may compromise the outcome of the study include lack of enrollment or the lack of RC events.

Figure 1. Study Flow-chart.

One-month minimum period for unblinded device familiarization

## 5.1 Duration

Each patient will be in the study for a maximum period of 72 hours.

Each participating site may involve one or more wards, based on its distribution of surgical high-risk patients. The study is expected to last approximately one year.

## 5.2 Rationale

There are few data in the literature on the incidence of RC in high risk surgical patients continuously monitored on a general ward in Europe. This pilot study will collect data on a high number of patients monitored by capnographic and/or SpO2 monitoring, thus allowing quantification of the incidence of respiratory markers and their correlation with cardiopulmonary or other complications in clinical practice and the related clinical and workflow impact.

The study will also allow evaluation of two different monitoring devices coupled with a remote patient monitoring system in terms of sensitivity and patients' compliance.

---

## 6. Product Description

All devices used in this study are commercially available (CE-Marked) and used within intended use in Europe. The Instruction for Use (IFU) manual is provided with the product in local country language.

The Capnostream monitoring system includes a capnograph/pulse oximeter monitor, sampling line for end tidal carbon dioxide (etCO2), and pulse oximetry sensor for measuring the peripheral oxygen saturation of arterial hemoglobin (SpO2).

Table 1 provides a list of commercially available products that may be used in the study.

**Table 1. Medtronic Market-Released Devices and Accessory Components**

Model or Version	Product	Manufacturer
CS08651-02	Capnostream™ 20p Portable Bedside Monitor Capnograph/Pulse Oximeter	Oridion Medical
Version 1.1	Capnostream Software	
Vital Sync™ 2.4 or future CE-marked available versions	Vital Sync™ Virtual Patient Monitoring Platform	Medtronic
Smart CapnoLine H Plus Smart CapnoLine H CapnoLine H CapnoLine H O 2 Smart CapnoLine Plus Smart CapnoLine O 2 /CO 2 Nasal FilterLine	etCO 2 Sampling Line for Microstream™ – enabled capnography monitors (mono use)	Oridion Medical
PM1000N-RR	Nellcor™ Bedside Respiratory Patient Monitoring System Pulse Oximeter, with Nellcor™ Respiration Rate (RR) parameter; intended for the continuous, non-invasive monitoring of respiration rate.	Covidien llc.
OxiMax Max-A OxiMax Max-AL OxiMax MaxN MaxFast SoftCare	Nellcor™ SpO 2 Sensor (mono use)	Covidien llc.
	Additional Accessories Roll Stand Assembly Vesa mounting plate Manfrotto clamp Power Supply kit (Main Electrical Power Cord with AC adapter) Battery Pack Extra battery / charger 3.15 Amp Type F fuses FilterLine Starter Kit Sensor extension cables (4, 8, or 10 feet) SpO 2 Sensor Pack	

[figure not shown]
## 6.1. Capnostream Monitor

The Capnostream monitor and its accessories provide continuous, non-invasive measurement and monitoring of:

- End-tidal carbon dioxide (etCO2) - level of carbon dioxide in exhaled breath.
- Respiratory rate (RR) – breaths per minute.
- Peripheral oxygen saturation of arterial hemoglobin (SpO2)
- Pulse rate (PR) – pulsatile cycle in beats per minute via pulse oximeter technology

The device also provides an Integrated Pulmonary Index™ (henceforth referred to as IPI) value, which is a numerical value that integrates four major parameters measured by Capnostream in order to provide a simple indication of the patient's ventilatory status. The integrated parameters are etCO2, RR, SpO2, and PR. Only these four parameters are used to calculate IPI; other parameters are not taken into account.

Figure 2. Capnostream 20p Portable Bedside Monitor

[figure not shown]
## 6.2. Vital Sync™

The Medtronic Vital Sync™ Informatics Manager & Virtual Patient Monitoring Platform is an FDA cleared and CE marked medical device. The Vital Sync™ Informatics Manager is the software that is intended to route and store medical device data and device diagnostic information from supported devices to the Electronic Medical Record (EMR) and Clinical Information System (CIS). The Vital Sync™ Virtual Patient Monitoring Platform is a remote monitoring platform that displays physiologic data, waveforms and alarms routed through the Vital Sync™ Informatics Manager for supported devices. The Capnostream 20p and PM1000N-RR are supported devices on this system. Patient information, generated during

Capnography and Pulse-Oximetry monitoring is transmitted wirelessly from the bedside devices to the hospital's server. The Vital Sync™ software, which can reside on hospital's server, takes this information and makes it viewable on any web-enabled device on the hospital network including a workstation or a Microsoft Surface tablet in case of nurse mobility. The information is formatted into HL7 protocol and written into the hospital EMR. HL7 protocol includes Electronic Medical Records, Alarm forwarding and Clinical Reports. The EMR integration feature of Vital Sync™ software will not be used in this study. No information can therefore be retrieved from the hospital EMR by the software. Patient data required for EWS calculation will be manually inputted to allow a retrospective analysis.

For the purpose of the clinical study, the CE marked Vital Sync™ Version 2.4 or future CE marked versions will be installed at the 2 sites using a dedicated server computer to be provided either by the site themselves, or by Medtronic.

Figure 3. Vital Sync™ VPMP

[figure not shown]

### 6.3. End-tidal Carbon Dioxide (etCO2) Sampling Line

A sample of the exhaled gases are delivered from the patient (via a cannula) into the monitor for etCO2 measurement. The etCO2 sample line (also referred to as a filter line) is a disposable single use sampling line. Each study patient will be connected to the Capnostream monitor with an etCO2 sampling line.

Supplemental oxygen may also be delivered through the sampling line, as needed. Any supplemental oxygen, up to 5 lit/min, will be delivered per usual clinical practice. The supplemental oxygen is not provided through the monitor.

Figure 4. etCO2 Sampling Line

## 6.4. Nellcor™ Bedside SpO2 Patient Monitoring System

The Nellcor™ Bedside Respiratory Patient Monitoring System is a portable pulse oximeter intended for continuous non-invasive monitoring of:

- Peripheral oxygen saturation of arterial hemoglobin (SpO2)
- Pulse rate (PR) – pulsatile cycle in beats per minute via pulse oximeter technology
- Respiratory rate (RR) – plethysmography-derived

If the monitoring system detects an alarm condition, it provides both visual and audible alarms.

**Figure 5. Nellcor™ Bedside Respiratory Patient Monitoring System**

## 6.5. Peripheral Oxygen Saturation (SpO2) Sensor

Pulse oximetry is a non-invasive method of measuring the amount of hemoglobin saturated with oxygen or SpO2. Light emitting diodes (LEDs) emit red and infrared light. Changes in light absorption during the pulsatile cycle determine the SpO2.

The oxygen transducers (sensors) are available as a reusable or a disposable single use sensor.

Each study patient will be connected to the Nellcor or Capnostream monitor with a non-invasive SpO2 disposable sensor applied to a finger (index finger preferred).

**Figure 6. SpO2 Sensor**

## 6.6. Packaging

The devices used are all CE-Marked and will be provided with their standard packaging. Labelling of all the devices will be in local language.

## 6.7. Intended Population

The Capnostream™ 20p combined capnograph/pulse oximeter monitor and its accessories are intended to provide professionally trained health care providers with continuous, non-invasive measurement and monitoring of carbon dioxide concentration of the expired and inspired breath and respiration rate, and with continuous non-invasive monitoring of functional oxygen saturation of arterial hemoglobin (SpO2) and pulse rate. It is intended for use with neonatal, pediatric, and adult patients in hospitals, hospital-type facilities, and intra-hospital transport environments.

The Nellcor™ Bedside Respiratory Patient Monitoring System is a portable pulse oximeter intended for prescription use only as a continuous non-invasive monitor of arterial oxygen saturation (SpO2) and pulse rate of adult, pediatric, and neonatal patients during both no motion and motion conditions, and for patients who are well or poorly perfused. The monitoring system is intended for use in hospitals, hospital-type facilities, and during intra-hospital transport. The OxiMax SPD™ Alert (SPD) feature is intended only for facility-use care of adults to detect patterns of desaturation indicative of repetitive reductions in airflow through the upper airway and into the lungs.

## 6.8. Equipment

The participating site will receive at minimum the following study specific equipment:

- Two Capnostream monitors per site and accessories as described above in section 6.1
- Two PM1000N-RR monitors and accessories as described above in section 6.4
- Disposables for Capnostream and PM1000N-RR monitors, including etCO2 sampling lines and SpO2 sensors
- Vital Sync™ related equipment as described above in section 6.2
- As preferred by each site, a dedicated server may be provided to host the Vital Sync™ software
- Microsoft Surface tablets may be provided to hospital nurses for remote monitoring

Monitor's calibration information is provided in their respective manual. Any additional maintenance or cleaning procedures should follow the operator's institution guidelines.

## 6.9. Product Use

Disposition or use of product provided to the site by the study sponsor is for study patient use only.

## 6.10. Product Training Requirements

Product information will be included in the study training materials. A protocol for alarm management in Phase II, in agreement with hospital policy, will be developed and shared with nursing staff.

## 6.11. Product Receipt and Tracking

Medtronic will allow shipment of study devices prior to the Site Initiation Visit for training purposes only. Study devices should be used exclusively for patients enrolled in the study and can be used following official site activation from the Clinical Study Manager.

Participating sites will be provided with a sufficient number of Capnostream and Nellcor monitors. In addition, a sufficient number of etCO2 sample lines and SpO2 Sensors will be provided.

Single use products (see Table 1) will be provided initially to participating sites in line with the number of expected patients to be enrolled. All the study devices will be provided free of charge by the sponsor for the duration of the study and they should be used only in this clinical study according to the CIP. They may be directly shipped to the sites or through the Medtronic field representative.

The following records will be maintained by the site personnel at minimum for product delivery, receipt, use, disposal and return at each study center: dates, quantities, lot/serial numbers, patient ID, and expiration dates, as applicable.

## 6.12. Product Storage

Product provided to the site should be stored in a secured area with access limited to delegated study staff.

## 6.13. Product Return

Product provided to the site shall be returned at the end of the study (excludes consumable products that have been used during the course of the study). When returning the clinical study equipment the proper use of skids and pallets, as well as boxes or crates of the appropriate size and materials for their contents, will minimize damage to the equipment. Containers should be properly cushioned and braced for shock and vibration mitigation and adequately sealed and filled when possible with the weight evenly distributed.

Containers and inner pack material going out of the country should be used in conjunction with moisture-resistant material such as desiccant and barrier bags. Straps, seals and shrink wrapping help minimize pilferage of the equipment during transport.

## 6.14. Product Accountability

Reconciliation of product received, used, disposed and returned will be completed at the end of the study. Medtronic will perform periodic reconciliation of product to ensure traceability.

# 7. Selection of Patients

## 7.1 Study Population

The target study population consists of post-surgical patients of adult age at high risk of developing respiratory and cardiovascular events on the hospital ward.

## 7.2 Patient Enrollment

A patient is considered enrolled in the study once he/she signs the Informed Consent form and meets the inclusion/exclusion criteria.

The investigator will maintain a log of all patients enrolled in the clinical investigation. A Patient Identification and Enrollment Log is a document to keep a confidential list of names of all patients participating in the clinical study.

## 7.3 Inclusion Criteria

- Non-cardiac post-surgical patients at high risk of developing respiratory and cardiovascular events based on both ARISCAT and POSPOM scores.  
ARISCAT Score is an accurate risk score for predicting high or intermediate risk for postoperative pulmonary complications in patients undergoing surgery, calculated based on preoperative data such as on patient's age, preoperative SpO2, respiratory infection, anaemia, surgery type and duration.

POSPOM Score is an accurate risk score for predicting in-hospital mortality in patients undergoing surgery, calculated based on preoperative data such as on patient's age, planned surgery and presence of additional diseases or disorders.

In particular, to be enrolled a patient must have:

**POSPOM score  $\geq 24$**  ( $> 3$  times the mortality average risk);

**OR**

**ARISCAT score  $\geq 26$**  (High or intermediate risk for postoperative pulmonary complications).

- Adult age ( $\geq 18$  year old).
- Patient is able and willing to give informed consent.

## 7.4 Exclusion Criteria

1. Expected ward length of stay  $\leq 24$  hours.
2. Post-surgical patients with American Society of Anesthesiologists physical status (ASA PS) V or higher.
3. Ventilated or intubated patients.
4. Patient is unwilling or unable to comply fully with study procedures (including non-toleration of the capnography cannula or skin contact allergies to medical grade adhesives) due to any disease condition which can raise doubt about compliance and influencing the study outcome.
5. Patient is a member of a vulnerable population, including legal incapacity or evidence that a patient cannot understand the purpose and risks of the study, regardless of authorized representative support.
6. Patient is participating in another potentially confounding drug or device clinical study.

## 8. Study Procedures

### 8.1 Schedule of Events

Data will be collected for Screening, Enrollment Visit and Monitoring Period. Additional data will be collected for Adverse Events, Device Deficiencies and Protocol Deviations.

Data collection requirements are summarized in Table 2. The study site personnel must report all study specific Adverse Events and changes in status of these Adverse Events from time of enrollment until a patient exits the study.

# LIFEGUARD Clinical Investigation Plan

CIP ID: MDT17026

Version 2.0 19 Jun 2019

Page 31 of 66

Medtronic

**Table 2. Data Collection Requirements**

Data	Screening Evaluation	Enrollment	Monitoring	Study Exit	Survey (at the study end)
Informed Consent	X				
Inclusion/Exclusion Criteria Evaluation	X				
Medical History		X			
Demographic & Physical Examination		X			
Vital Signs		X	X		
Supplemental Oxygen Use		X	X		
Surgery Information		X			
Monitoring Duration			X		
Medications		X	X		
Number/type of staff interventions (alarm and non-related)			X		
Adverse Events		X	X	X	
Device Memory Data			X		
Patients' compliance			X		
Product Information			X		
Device Deficiencies			X	X	
Protocol Deviations	X	X	X	X	
Reason for Study Exit				X	
Date of Patient Discharge from Hospital				X	
Clinical staff's satisfaction and workflow impact					X

## 8.2 Patient Screening

A consideration of all potential patients is recommended to minimize selection bias. All potential patients, whether finally enrolled in the study or not, will be entered on the Screening Log.

If the patient is potentially eligible and willing to consider participation, written informed consent must be obtained. A review of patient's files by the investigator is required to determine preliminary eligibility according to inclusion and exclusion criteria. Information included on the Screening Log includes:

- Informed consent signature date, if applicable
- Inclusion / exclusion criteria evaluation

Patients will be considered a screen failure and immediately exited from the study if the patient signs the Informed Consent but fails to meet study inclusion/exclusion criteria prior to monitoring on the hospital ward. The reason for screen failure will be documented on the Screening Log. Premature exit from the study by a patient must be documented on the Study Exit eCRF.

## 8.3 Prior and Concomitant Medications

Medications relevant to the study (see Appendix C) will be listed in the eCRF. Details of relevant medications used during surgery and recovery will be collected at study enrollment and during the monitoring period. Medications will be administered to patients during the study according to hospital policy.

## 8.4 Patient Consent

The investigator or authorized designee must obtain written informed consent before any clinical study related activity takes place. Written informed consent must be obtained prior to surgery.

In advance of the consent discussion, the patient should receive the EC approved Patient Information and Informed Consent Form. During the consent discussion, the investigator or his/her authorized designee must fully inform the patient of all aspects of the clinical study that are relevant to the patient's decision to participate in the clinical study. If a patient is illiterate, an impartial witness must be present during the entire informed consent discussion. All items addressed in the Patient Information and the Informed Consent Form must be explained. The language used shall be as non-technical as possible and must be understandable to the patient and the impartial witness, where applicable.

The patient must have ample time and opportunity to read and understand the Patient Information and the Informed Consent Form, to inquire about details of the clinical study, and to decide whether or not to participate in the clinical study. All questions about the clinical study should be answered to the satisfaction of the patient.

Neither the investigator, nor the investigation site staff shall coerce or unduly influence a patient to participate or to continue to participate in the clinical study. The informed consent process shall not waive or appear to waive the patient's rights.

When the patient decides to participate in the clinical study, the Informed Consent Form must be signed and personally dated by the patient and investigator or authorized designee. If applicable, the witness shall also sign and personally date the consent form to attest that the information in the Patient Information and Informed Consent Form was accurately explained and clearly understood by the

patient, and that informed consent was freely given. Detailed documentation of the process must be recorded in the patient's case history.

After all persons have signed and dated the Informed Consent Form, the investigator must provide the patient with a copy of the Patient Information and the Informed Consent Form.

Medtronic will inform the investigators whenever information becomes available that may be relevant to the subject's confirmed participation in the clinical study. The investigator or his/her authorized designee should inform the patient in a timely manner.

Medtronic will revise the written Patient Information and Informed Consent Form whenever new information becomes available that may be relevant to the patient's confirmed participation in the clinical study. The revised information will be sent for approval by the EC. After approval by the EC, a copy of this information must be provided to the any patients that are still participating in the study and re-consent obtained if requested by the EC.

## 8.5 Enrollment

The point of enrollment is completion of informed consent and confirmation of inclusion/exclusion criteria per the screening evaluation.

Data collected for enrolled patients includes:

- Medical history (including surgical, apnea, and medical therapy such as oxygen use and opioid use)
- Demographic & Physical exam
- Vital signs
- Supplemental oxygen use
- Surgery information

## 8.6 Treatment Assignment

Patients will be randomly allocated 1:1 to either Capnostream™ 20p or Nellcor Monitoring Systems both in Phase I and in Phase II. The device allocation will be unblinded to both patient and physician.

The sequence of treatments will be randomly permuted in blocks of 2 or 4 patients per block. The blocked randomization will be centralized and schedules will be created by the study statistician using statistical software. The randomization will be performed by the center via the EDC system (Oracle Clinical). To minimize the selection bias, the randomization procedure will be unpredictable. In this study a center stratified blocked randomization will be used, so that a separate permuted block randomization will be performed for each center. This guarantees treatment balance within strata.

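### Block sizes of 2 or 4 per centre, printed in the CIP and used with open device allocation, do not give the unpredictability that CIP 8.6 claims

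*Protocol*

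**What the plan says.** CIP 8.6 (Treatment Assignment) sets 1:1 allocation to the two monitoring systems in both phases and describes the method in one paragraph:

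- Block sizes: "The sequence of treatments will be randomly permuted in blocks of 2 or 4 patients per block". It does not say whether the two sizes are mixed at random or one of them is used throughout.
- Stratification is by centre only, "so that a separate permuted block randomization will be performed for each center".
- Openness: "The device allocation will be unblinded to both patient and physician".
- Concealment: "The blocked randomization will be centralized and schedules will be created by the study statistician using statistical software", and "The randomization will be performed by the center via the EDC system (Oracle Clinical").
- Claimed property: "To minimize the selection bias, the randomization procedure will be unpredictable".

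Other sections bear on this. CIP 14.7.1 lists the CIP among the records the investigator keeps, so those who enrol have the block sizes. CIP 5 gives the purpose of randomising as similar patient groups on the two devices. CIP 12.3 plans to analyse the difference between the two groups within each phase, whereas SAP 7.1.1 says that the arms will not be compared. CIP 7.4, criterion 4, excludes patients unable to comply with study procedures, "including non-toleration of the capnography cannula or skin contact allergies to medical grade adhesives". The SAP repeats the open 1:1 allocation (5.3) and adds no detail on the randomisation.

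**The concern.** A central schedule released through the EDC hides the list. It does not hide what can be worked out from allocations already made. With short blocks of known size, separate sequences per centre and devices in plain view, a recruiter who keeps count can often tell which device is likely next and sometimes knows it for certain.

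That matters when entry involves judgement that differs by device. Cannula tolerance bears in practice on Capnostream only. A recruiter who expects Capnostream next could judge a borderline patient unsuitable, or wait. Were this to happen, the Capnostream arm would lose a particular kind of patient and the Nellcor arm would not. The primary result is reported separately by arm, so any comparison of the two arms would carry that difference.

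**Working it through.** The plan gives no figure for predictability, so there is none to reproduce. Two measures are used: the share of allocations **certain** beforehand, and the share **guessed correctly** by someone who always names the arm that is behind and tosses a coin when the arms are level. Pure chance gives 50% on the second.

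**Inputs.** Sizes 2 or 4, 1:1, one sequence per centre (CIP 8.6). Phase I has 70 patients at two centres (CIP 5). An equal split, 70/2 = 35 per centre, is an assumption, since the 50% cap per site applies to total enrolment. The guesser is assumed to see the whole ordered sequence at the centre and to know the size set. This gives an upper bound.

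**Fixed size 2.** The second patient of each block is certain. In 35 patients there are 17 full blocks and one further patient.
- Certain: 17/35 = 49%.
- Correct: (17 × 1.5 + 0.5)/35 = 26/35 = 74%.

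**Fixed size 4.** The fourth patient is always certain, and the third is certain when the first two match (probability 1/3). That is 4/3 certain allocations per block. Expected correct guesses per block are 1/2 + 2/3 + 2/3 + 1 = 17/6. In 35 patients there are 8 full blocks and three further patients.
- Certain: (8 × 4/3 + 1/3)/35 = 11/35 = 31%.
- Correct: (8 × 17/6 + 11/6)/35 = 24.5/35 = 70%.

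**Sizes 2 and 4 mixed at random.** Let q be the probability of size 2; it is not stated, so q = 1/2 is an assumption. Certainty arises only when a block of 4 opens with two patients on the same arm (probability 1/3), and then its last two allocations are known. Mean block length is 4 − 2q.
- Long-run share certain = (1 − q)(1/3)(2)/(4 − 2q).
- Long-run share correct = 1/2 + (1/2) × [q + (1 − q)(5/3)]/(4 − 2q). The bracket counts the points in a block at which the arms are level.

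| q (probability of size 2) | Certain | Correct |
|---|---|---|
| 1/3 | (4/9)/(10/3) = 13.3% | 71.7% |
| 1/2 | (1/3)/3 = 1/9 = 11.1% | 13/18 = 72.2% |
| 2/3 | (2/9)/(8/3) = 8.3% | 72.9% |

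Simulated sequences of 35 at q = 1/2, with a guesser who updates exactly on all earlier allocations, give 10.8% certain and 71.5% correct. At 105 per centre the figures are 11.0% and 72.0%. The small shortfall at 35 comes from the cut-off last block.

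**Larger mixed sizes, for comparison.** Sizes 4, 6 and 8 in equal proportion, again by simulation of 35 patients: about 2% certain and 67% correct.

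**In patients.** For 35 at one centre with the equal 2/4 mix, 0.108 × 35 is about 3.8 certain allocations. With 4/6/8 it is 0.023 × 35, about 0.8. By symmetry about half of these would be Capnostream, so roughly two Capnostream allocations per centre in Phase I are certain now.

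**The case against.** The strongest reply is that CIP 8.6 describes concealment: a central list, two possible block sizes and release through the EDC. Every permuted-block design fails a 50% guessing standard, including the alternative above at about 67%. A reader might infer that the section flatly contradicts itself. That goes too far, because the sentence can be read as a statement about hiding the list. What stands is narrower: with the sizes disclosed and allocation open, the procedure is more predictable than it need be on every reading of the sizes, and the wording promises more than it delivers.

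A reader might also infer that recruiters know every past allocation. The CIP says only that patient and physician know the device. A centre may use several wards (CIP 5.1), so no single person need see the ordered sequence. The percentages are therefore upper bounds.

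Nor do the documents show that selection occurs. CIP 8.2 puts every potential patient on the Screening Log with the eligibility evaluation, so holding patients back would leave a trace. CIP 8.5 makes confirmation of eligibility part of enrolment, ahead of assignment in 8.6. Criterion 4 is tied to a disease condition and applies to all patients; expected dislike of the cannula is not a listed ground. However, no section says that the EDC withholds the allocation until eligibility is entered.

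Finally, the arms do not share an endpoint (four markers against two, CIP 4.1.1), so their proportions are not like for like in any case. This limits the stakes but does not remove them while CIP 12.3 still plans a between-group analysis.

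**Conclusion.** The point holds as a minor one. CIP 8.6 claims a property that blocks of 2 or 4, disclosed to sites and run within centre with open allocation, do not provide. For a recruiter with full sight of the centre's sequence, and an assumed 35 patients per centre in Phase I, about 72% of allocations are guessable and about 11% certain under an equal random mix. The certain share is 8% to 13% for mixes from 1/3 to 2/3, and 31% or 49% under a fixed size of 4 or 2.

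The consequence is a possible, undemonstrated loss of comparability between the device arms, which is the stated aim of randomising in CIP 5 and the basis of the between-group analysis in CIP 12.3. If SAP 7.1.1 governs and the arms are not compared, the impact is small. A reader might extend the point to the Phase I versus Phase II comparison. That comparison is not randomised, so block size is not what threatens it.

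**What to change.** 1. Generate the remaining schedule with larger block sizes varied at random. Sizes 4, 6 and 8 are one example, not the only sound choice.
2. Keep the sizes only in the restricted randomisation file and delete them from CIP 8.6.
3. Replace the claim of unpredictability with a statement that the list is concealed and block sizes are withheld from sites.
4. Have the EDC release an allocation only after the eligibility confirmation already required by CIP 8.5 has been entered.

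The cost is a new schedule, a short CIP amendment and an EDC ordering check. The benefit is mainly fewer certain allocations, from about 11% to about 2% under the equal-mix assumption; the guess rate falls only from about 72% to 67%. The downside is arm imbalance of up to 4 per centre and phase (half of the largest block, 8/2), against up to 2 (4/2) now. Check this against the monitors available, since CIP 6.8 guarantees each site only two of each type. If the schedule can no longer be changed, items 3 and 4 can still be adopted in part: describe the concealment accurately, without claiming that sizes were withheld, and add the EDC check.
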